**e. Study Organization**

This is a multicenter study with University of Massachusetts Medical Center as the lead center and [name] as PI. [name] will serve as the site PI at Boston Children's Hospital and oversee the study at this location. Monitoring will be performed at each site. De-identified data from both sites will be stored in the RedCap database.

**f. Data and Safety Monitoring Plan**

A Data Safety and Monitoring Board (DSMB) will provide oversight for this study. The DSMB will be constituted to oversee the safety of patients on this trial. The DSMB will meet after the first 8 patients have been enrolled, and subsequently not less than twice yearly. The DSMB will include 2 neonatologists (not associated with the study) and two pediatric pulmonologists (not associated with the study) as well as one primary pediatrician from the community (also not associated with the study). We will also include a member of our Parent Advisory Board, a parent of a premature infant who had required oxygen supplementation in the home in the past.

At the beginning of each meeting, [name] and the primary research coordinator will be present to discuss study enrollment and any issues, and then they will leave the meeting so the DSMB can review

any adverse events. If one of the arms is noted to have more than 3 respiratory re-hospitalizations, the committee will come together and decide what, if any part of the study needs to be altered and/or stopped.

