**Serious Adverse Events (SAE):**

A serious adverse event is an undesirable sign, symptom or medical condition which:

- is fatal or life-threatening
  - Non-infectious hypoxic events or Acute Life Threatening Events (ALTEs) between and during monthly clinic visits
  - Development of newly diagnosed pulmonary hypertension.

OR

- results in persistent or significant disability/incapacity

OR

- requires inpatient hospitalization or prolongation of existing hospitalization, unless hospitalization is for one of the following:
  - routine treatment or monitoring of the studied indication, not associated with any deterioration in condition
  - elective or pre-planned treatment for a pre-existing condition that is unrelated to the indication under study and has not worsened since the start of study drug
  - treatment on an emergency outpatient basis for an event not fulfilling any of the definitions of a SAE given above and not resulting in hospital admission
  - social reasons and respite care in the absence of any deterioration in the patient's general condition

OR

- is medically significant, i.e., defined as an event that jeopardizes the patient or may require medical or surgical intervention to prevent one of the outcomes listed above

**SAE Reporting:** Information about all serious adverse events will be collected and recorded. To ensure patient safety, each serious adverse event must also be reported to the PI as soon as possible after learning of its occurrence

At BCH, according to its IRB policies, Serious Adverse Events that are **serious, unexpected and related** to the study, including rehospitalizations and emergency department visits will be reported to the study's DSMB and IRB promptly (within 72 hours of occurrence). At all other sites, the SAE reporting will comply to the site specific IRB policies. New diagnoses of pulmonary hypertension will similarly be reported to the DSMB and IRB within 72 hours of diagnosis. All Adverse events and Serious Adverse events will be presented to the DSMB board every 6 months.

i. **If the Investigator is the Sponsor/Assignee (IND or IDE-holder), he/she is responsible for selecting a qualified monitor who will monitor the progress of all clinical investigations conducted under the IND or IDE. Please describe the monitoring plan for this protocol below:**

↳ Note: the EQuIP office provides monitoring services and advice. For info, contact EQuIP @ [name].

Not applicable

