**Stopping Rules:**

The study will be stopped, if there are least 3 *related* respiratory related hospitalizations in one arm *and* the majority of the DSMB votes that these are study related and cannot be remedied.

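### The DSMB's stopping count can be met without triggering a meeting, and its review trigger has no denominator or between-arm comparison

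*Combined protocol and SAP*

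**What the plan says.** Section 5f (Data and Safety Monitoring Plan) sets the scheduled meetings: "The DSMB will meet after the first 8 patients have been enrolled, and subsequently not less than twice yearly". It adds an ad hoc trigger: "If one of the arms is noted to have more than 3 respiratory re-hospitalizations, the committee will come together". At that meeting the board is to "decide what, if any part of the study needs to be altered and/or stopped". The trigger does not require the events to be judged related.

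The Stopping Rules that follow read "The study will be stopped, if there are least 3", and then restrict the count to related respiratory hospitalizations in one arm. They add a second condition, that "the majority of the DSMB votes that these are study related and cannot be remedied".

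Section 4h (SAE Reporting) has serious, unexpected and related events at Boston Children's Hospital (BCH), re-hospitalizations included, go to the "DSMB and IRB promptly (within 72 hours of occurrence"). For the rest: "At all other sites, the SAE reporting will comply to the site specific IRB policies". As a routine, "All Adverse events and Serious Adverse events will be presented to the DSMB board every 6 months".

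None of these sections gives an expected rate of respiratory re-hospitalization, a denominator, a time window, a between-arm comparison or an error rate for either count.

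**The concern.** There are two separate weaknesses.

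The first is a gap between the rules. The ad hoc meeting needs a fourth event, while the stopping count can be complete at the third. Stopping also needs a vote, and a vote needs a meeting. At exactly three events, all related, nothing in the plan calls that meeting before the next scheduled one.

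The second is that the review trigger is a bare count in one arm. It is the same when 8 infants are enrolled as when 196 are, and it takes no account of what the other arm shows. If respiratory re-hospitalization is common in this population, four events in an arm will arrive whether or not oxygen management does harm. Respiratory re-hospitalization is one of the outcomes chosen to show that home-oximetry weaning is not less safe (Section 4e), so the prompt for reviewing it ought to carry information.

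Uneven reporting adds to both. Outside BCH, the document states no deadline by which a related event must reach the board.

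**Working it through.** The plan states no operating characteristic for either rule, so there is no figure of its own to reproduce.

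**Inputs from the documents.** Review trigger: 4 or more respiratory re-hospitalizations in an arm (Section 5f). Stopping count: 3 or more related ones in an arm, plus the vote (Stopping Rules). Arm size: 98 (Section 5d). BCH enrolment: 68 of 196 (Abstract). Counting window: first clinic visit to 6 months after home oxygen ends (Section 4e).

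**Assumed inputs.** p, the share of infants with a respiratory re-hospitalization over that window: 1% to 20%. q, the share of such events judged related: 10% to 100%. The documents give neither. The 30% and 40% in Section 5d are for emergency department visits and are not used here.

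**Step 1: how often the stopping count comes first.** Related events are a subset of all events. The stopping count is reached before the fourth event only if the first three are all related. Treating relatedness as independent between events, the chance among arms that reach three events is q³:

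- q = 10%: 0.1%
- q = 25%: 1.6%
- q = 50%: 12.5%
- q = 100%: 100%

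Otherwise the review trigger fires before the stopping count or at the same event.

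**Step 2: how often the review trigger fires with no harm.** For one arm, P = 1 − Σ C(98,k) pᵏ(1−p)⁹⁸⁻ᵏ, summed over k = 0 to 3. At p = 5% the four terms are 0.0066, 0.0338, 0.0864 and 0.1455. They sum to 0.272, so P = 0.728. With equal rates, P for both arms is P², and for at least one arm 1 − (1−P)².

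| Assumed p | One given arm | At least one arm | Both arms |
|---|---|---|---|
| 1% | 1.7% | 3.4% | <0.1% |
| 2% | 13% | 25% | 2% |
| 5% | 73% | 93% | 53% |
| 8% | 96% | 99.8% | 92% |
| 10% | 99.1% | >99.9% | 98% |
| 20% | >99.9% | >99.9% | >99.9% |

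The one-arm probability passes 50% at p = 3.7% and 95% at p = 7.7%. This counts infants with at least one event; repeat admissions would bring the trigger sooner.

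**Step 3: whether it responds to harm.** If the true rate in an arm doubles, the one-arm probability moves as follows:

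- 1% to 2%: from 1.7% to 13%
- 2% to 4%: from 13% to 55%
- 5% to 10%: from 73% to 99.1%
- 10% to 20%: from 99.1% to about 100%

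**Step 4: part-way through.** At 49 per arm and p = 10%, one given arm fires with probability 73.5%. At least one arm: 1 − 0.265² = 93%. Both arms: 0.735² = 54%.

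**Step 5: reporting coverage.** 196 − 68 = 128 infants (65%) are at sites with no DSMB deadline stated here for serious, unexpected, related events.

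**The case against.** The strongest reply is that the two counts measure different things and work in sequence. A reader might infer that the review trigger is simply looser than the stopping rule. The documents do not support that: one counts all respiratory re-hospitalizations and the other only related ones, so the wider count normally comes first. This stands, and it reduces the gap to the q³ case.

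A reader might also infer that both rules are bare counts unable to tell harm from background. That is wrong for stopping, which requires a judgement of relatedness and a majority vote. Case-by-case adjudication is a real safeguard, although it is weak against harm that appears as an excess of ordinary respiratory admissions.

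A low-threshold prompt for discussion is a defensible cautious choice. Nothing prevents the board from comparing arms, and enrolment is discussed at each meeting. But the plan does not require rates by arm to be supplied.

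It would also be too strong to say that three events lead to no meeting at all. Scheduled meetings continue, and the vote implies that the board confers. What is missing is a stated prompt.

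On reporting, the form asks for answers specific to BCH, which may explain the BCH-only deadline. SAEs must reach the PI as soon as possible without limit to one site, and there are monthly calls with all site PIs (Section 4f). So the events need not go unnoticed. The step from the PI to the board still has no stated time for the other sites.

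**Conclusion.** The point holds as a defect in the review prompt and in how the two passages fit together. The plan can leave a met stopping count without a prompt meeting. That is uncommon if few events are judged related and more likely if many are; the size depends on q, which is assumed, and on independent relatedness judgements.

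The review trigger carries little information at background rates of about 8% or more, where it fires in at least 96% of arms of 98 without harm. At 1–2% it discriminates to some degree. Since the documents give no rate, the claim that the trigger never gives a signal is not supported. Nor can the 93% at half enrolment be read as both arms crossing: it is the chance for at least one arm, and both cross with probability 54%. Nothing here implies that the trial would stop automatically.

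**What to change.** 1. Reconcile Section 5f and the Stopping Rules on count and event definition, so that reaching the stopping count always convenes the board. The investigators and the board should settle which counts apply. A lower review count alone would make the second weakness worse: at p = 5%, the chance of 3 or more events in an arm of 98 is 87%, against 73% for 4 or more.
2. State an expected background rate of respiratory re-hospitalization, with its source.
3. At each review, give the board respiratory re-hospitalizations per infant or infant-month by arm, with the between-arm difference and its confidence interval. Keep the count as a prompt and leave any threshold on the difference to the board.
4. State one DSMB notification time for serious, unexpected, related events, applying at all nine sites.

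The cost is protocol and charter wording, tabulation of follow-up time by arm at the coordinating centre, and perhaps a few more ad hoc meetings. The sample size and the efficacy analyses are unaffected.

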**Stopping Rules:**

The study will be stopped, if there are least 3 *related* respiratory related hospitalizations in one arm *and* the majority of the DSMB votes that these are study related and cannot be remedied.

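### A home death or life-threatening event obliges no DSMB review, and outside Boston Children's Hospital its only stated route to the board is the scheduled meetings and six-monthly presentation

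*Combined protocol and SAP*

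**What the plan says.** Three parts of the plan bear on this.

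**Convening (section 5f, Data and Safety Monitoring Plan).** The remit is general: "The DSMB will be constituted to oversee the safety of patients on this trial". The board meets after the first 8 infants are enrolled and "subsequently not less than twice yearly". One event-based trigger is given: "If one of the arms is noted to have more than 3 respiratory re-hospitalizations, the committee will come together".

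**Stopping (section 5f, Stopping Rules).** The study stops if there are at least 3 related "respiratory related hospitalizations in one arm" and most of the board votes that these are due to the study and cannot be put right.

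**SAEs and their reporting (section 4h).** Fatal and life-threatening events are SAEs. Listed beneath them are "Non-infectious hypoxic events or Acute Life Threatening Events (ALTEs) between and during monthly clinic visits" and "Development of newly diagnosed pulmonary hypertension". On reporting:
- At every site, "each serious adverse event must also be reported to the PI as soon as possible after learning of its occurrence".
- At BCH, SAEs that are "serious, unexpected and related" go to the DSMB within 72 hours. Rehospitalizations and emergency department visits are expressly included.
- Other sites follow their own IRB policies. No DSMB deadline is stated for them.
- New pulmonary hypertension goes to the DSMB within 72 hours of diagnosis.
- All adverse events and SAEs are presented to the DSMB every 6 months.

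**The concern.** The RHO arm allows oxygen to be reduced at home between monthly visits and replaces polysomnography with home recording before oxygen is stopped. If weaning goes too fast, the direct harm is hypoxia at home, and section 4h recognises this in its list of SAEs. The escalation rules then look only at respiratory admissions. A death at home, or a life-threatening event that does not lead to such an admission, adds nothing to either rule.

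What is at stake is the timing of independent review. Whether a home death is related to a weaning strategy is a judgement the independent board should be able to make early, while other infants are still being weaned under the same criteria. The plan makes a fourth respiratory re-hospitalization in one arm a mandatory occasion for review. It leaves a home death to the board's discretion, and the board can use that discretion only once it has been told.

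**Working it through.** The thresholds carry no derivation or operating characteristic, so there is no stated figure to reproduce. The check sets the rules side by side and then does some short arithmetic on reach and delay.

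**Step 1. What each event does under the rules as written.** *Scheduled* means the DSMB meetings and the six-monthly presentation. The last three rows are events without a respiratory admission.

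| Event | Adds to convening count (more than 3 per arm) | Adds to stopping count (at least 3 per arm) | Stated DSMB timing |
|---|---|---|---|
| Respiratory re-hospitalization | 1 | 1 if related | BCH: 72 hours if unexpected and related; otherwise scheduled |
| Home death | 0 | 0 | BCH: 72 hours if unexpected and related; otherwise scheduled |
| ALTE or non-infectious hypoxic event meeting the SAE definition | 0 | 0 | As for a death; a related, unexpected emergency visit at BCH is inside the 72-hour route |
| New pulmonary hypertension | 0 | 0 | 72 hours from diagnosis |

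The timing gap therefore concerns deaths and life-threatening events, and not pulmonary hypertension.

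**Step 2. How many infants are outside the BCH route.** Section 1 gives 196 infants in total, 68 of them at BCH.
- Other sites: 196 − 68 = 128, and 128/196 = 65.3%.
- BCH: 68/196 = 34.7%. For these infants the 72-hour route applies only when the event is judged both unexpected and related.

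**Step 3. How long the wait can be.** Take six-monthly presentations, evenly spaced, with no earlier notice to the board.
- Longest wait: 365/2 = 182.5, about 182 days.
- Average wait if events fall evenly across the interval: 182/2 = 91 days.
- Section 5d anticipates an RHO duration of 108 days. Since 182 > 108, an infant enrolled just after an event could finish weaning before the board sees that event. Since 91 < 108, this describes the long end of the range and not the typical case.

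**Step 4. Does the stopping rule exclude other grounds?** Three related home deaths in one arm would count as 0 under the Stopping Rules. But the text gives a condition under which the study stops. It does not say this is the only one, and a met count still needs the majority vote. What is missing is a pre-specified prompt for the board to act. Its authority to act is not in question.

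**Step 5. Should hypoxic events be added to the count of 3?** Arm B sends at least 25 hours of recorded oximetry every 4 to 7 days. Arm A is recorded with the study device only around the polysomnogram. The SAE definition gives no depth or duration for a hypoxic event. A per-arm count that included such events could reach 3 in Arm B because more is recorded there.

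**The case against.** The case for leaving the plan alone is substantial in places.

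- **This is a BCH form.** Its instructions ask for answers specific to BCH and name adverse event reporting. Other sites' policies, any DSMB charter and the lead centre's own submission are not in the file. This stands as a limit. The 128 infants are those for whom this document states no expedited DSMB deadline, and a reader should not infer that their sites have none. It does not remove the point, because section 4h itself says how the other sites report and the board oversees the whole trial.
- **The BCH route is wider than it may look.** It includes related, unexpected emergency visits, and a related, unexpected home death also falls within it. This stands. The gap left at BCH is events judged expected or unrelated.
- **The board can act anyway.** It has a general remit, a minimum and not a maximum number of meetings, and an early meeting after 8 infants. This disposes of most of any complaint about the stopping count. It does not settle when the board is told.
- **Other safeguards exist.** The PI hears of every SAE as soon as possible, there are monthly calls with site PIs, an investigator may withdraw an infant, each infant keeps a clinical monitor, and each wean must meet saturation criteria. These reduce risk. None of them is independent review, and none sets a time for onward notice to the DSMB.
- **No event rate is given.** This is correct. The documents do not allow the frequency of deaths or life-threatening events without a respiratory admission to be estimated.

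**Conclusion.** The concern holds as a gap in reporting deadlines and mandatory review. For a death or life-threatening event at a non-BCH site (128 of 196 infants, 65%), or at BCH when judged expected or unrelated, the only stated DSMB timing is the scheduled meetings and six-monthly presentation. The wait is at most about 182 days, and about 91 on average if events fall evenly and presentations are evenly spaced. No such event obliges the board to convene.

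Three stronger readings are tempting, and the documents do not support them:
- That the trial could not be stopped for deaths. The stopping rule is not worded as exclusive, and the board's remit is general.
- That the board would typically wait six months. That is the maximum, and there is also an early meeting after 8 infants.
- That deaths, ALTEs and hypoxic events should all simply be added to the count of 3. For hypoxic events this would mix harm with intensity of recording.

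No endpoint, sample size or analysis is affected. The change should be made because the possible consequence is late independent review of an infant death and the remedy is a few sentences.

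**What to change.** 1. **Section 4h, SAE Reporting, add:** *All sites report any death, and any life-threatening event (including an ALTE or non-infectious hypoxic event that meets the SAE definition), to the DSMB within 72 hours, whether or not judged expected or related.* This follows the model the plan already uses for new pulmonary hypertension.
2. **Section 5f, Data and Safety Monitoring Plan, add:** *Any death, and any such life-threatening event or new pulmonary hypertension that the DSMB chair considers possibly related, prompts an ad hoc DSMB review, by call if the board chooses.*
3. **Section 5f, Stopping Rules, add only:** *This rule does not limit the DSMB's power to recommend stopping for other events, including a single related death.* Leave the count of 3 related respiratory hospitalizations and the majority vote as they are, and do not add hypoxic events to the count.

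**Cost.** A few sentences of protocol wording, one 72-hour notice per event from the site concerned, and some extra ad hoc calls. The board already exists and the events are already collected as SAEs. The number of extra calls cannot be estimated from the documents. Screening by the chair in item 2 limits calls for life-threatening events and pulmonary hypertension that are clearly unrelated.

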**6. Risks and Discomforts**

By definition, patients enrolled in the “Standard Therapy” arm will not have additional risk from usual practice. Infants in the “RHO” arm may have changes made in their oxygen delivery between clinic visits. However, these infants will continue to have their clinically-indicated, NICU-supplied monitors to ensure safety, and weans will have been made using patient data. We therefore believe patients enrolled in the “RHO” arm will have less risk compared to the standard care.

Patients in the “RHO” arm will have an additional oximetry probe, identical to the ones utilized for their clinically-indicated oximeter. These will be rotated every 12 hrs. Theoretically, if left on the same area for extended periods without rest, probes can cause skin irritation. In their use in the NICU and in the CHILD clinic with thousands of infants, this complication has not been realized.

We will also instruct each family to use different sites for the probes to minimize risk.

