## **1. Abstract**

This research protocol describes a randomized control trial to compare two different methods of managing home oxygen therapy in premature infants. This is a multicenter study involving 9 centers. We plan to enroll a total of 196 infants, of which 68 will be from Boston Children's Hospital (BCH). The current standard for oxygen management includes brief assessments of a patient's oxygen saturation status during monthly clinic visits. The patient's oxygen status between visits is assumed to be acceptable; although it is possible for significant hyperoxia or hypoxia to occur, providers have no data to help with decision-making. In many centers, final steps before discontinuing home oxygen therapy (HOT) often include polysomnography (PSG), which can be costly and requires the inconvenience of rehospitalization. Advances in data storage and pulse oximetry technology have expanded potential uses for recorded home oximetry (RHO) in the accurate assessment of hypoxemia. At Boston Children's Hospital, we have pioneered the use of recorded home oximetry (RHO) in other research protocols, and shown that it can be a simple and convenient method for parents to transmit oximetry data to providers.

In this trial, we will randomize premature infants who require HOT at time of discharge from the NICU, who are referred for follow-up at the Center for Healthy Infant Lung Development. At the time of their first outpatient appointment, infants will be randomized to one of two treatment arms:

**Arm A (“Standard therapy”):** Infants' oxygen will be increased, decreased, or maintained based on brief structured assessments during monthly clinic visits. Polysomnograms will be utilized prior to final discontinuation of oxygen. RHO will only be utilized on the night prior to and during the polysomnogram to compare these two modalities.

**Arm B (RHO):** Infants will have the same monthly clinic assessments as in Arm A, but also will utilize RHO to potentially increase, decrease or maintain oxygen between monthly visits. Parents will transmit a minimum of 25 hours (1500 minutes) of stored RHO data (approximately 4 days, 8 hours per day) every 4-7 days. Changes in oxygen needs will be made based on standardized objective criteria. To determine discontinuation of oxygen, RHO will be utilized instead of polysomnography.

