During the 4-7 day evaluation periods to determine readiness to wean or status post wean, parents will be instructed to use the oximeter continuously during nocturnal sleep periods for a minimum of 25 hours (1500 mins/approximately 8 hours per day for 4 days). At the end of the 4-7 day period, data will be downloaded and electronically sent via secure email. For families who do not have access to a computer, and/or are uncomfortable with technology we will provide with data cards that can then be sent via provided protected express shipping envelopes with postage. All data cards will be sent to [name] at UMass for analysis as soon as they are removed from the oximeter.

Over the 4-7 days, a minimum of 25 hours (1500 minutes) of data is to be sent to UMass and deemed interpretable before any change in supplemental oxygen management is made. If the data is deemed inadequate or unreadable, the parent will be notified and no change in oxygen management will be made. Infants randomized to routine care will be weaned at monthly outpatient clinic visits per structured clinic-based protocol. Weaning parameters for each arm are listed in Table 1.

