**Table 1.**  
**O2 WEANING PARAMETERS**

	STANDARD OXYGEN MANAGEMENT ARM	CpOx OXYGEN MANAGEMENT ARM
CRITERIA FOR INCREASING O2 FLOW RATE	INABILITY TO MAINTAIN O2 SAT >93% AT PATIENT'S CURRENT O2 LEVEL FOR 20 MINUTES IN CLINIC VISIT CHALLENGE	INABILITY TO MAINTAIN O2 SAT >93% FOR >95% OF RECORDED TIME
CRITERIA FOR MAINTAINING CURRENT O2 FLOW RATE	ABILITY TO MAINTAIN O2 SAT >93% AT PATIENT'S CURRENT O2 BUT UNABLE TO MAINTAIN O2 SAT >93% AT WEANED FLOW RATE FOR 20 MINUTES IN CLINIC VISIT CHALLENGE	ABILITY TO MAINTAIN O2 SAT >93% FOR >=95% OF RECORDED TIME BUT UNABLE TO MAINTAIN O2 SAT >96% FOR >=95% OF RECORDED TIME
CRITERIA FOR WEANING O2 FLOW RATE	ABILITY TO MAINTAIN O2 SAT >96% AT WEANED FLOW RATE FOR 20 MINUTES IN CLINIC VISIT CHALLENGE	ABILITY TO MAINTAIN O2 SAT > 96% FOR >=95% OF RECORDED TIME

\* Clinic pass and fail will be determined per clinic assessment of oximeter alarms.

\*\* CpOx pass and fail will be determined by assessment of recorded oximetry. A minimum of 4 days of data, with a minimum of 8 hours per day, will be required for analysis to make any wean.

For infants in both arms, O2 weaning will proceed, when allowable per weaning criteria in the protocol, in 50% increments to a minimum of 125 cc/min. (For example, flow rate of 500 cc/min will be decreased to 250 cc/min, and 250 cc/min will be decreased to 125 cc/min.) Once infants achieve flow rates of 125 cc/min (or if they are discharged home from NICU on <125 cc/min), the next weaning step will be to room air during the day and nocturnal O2 only at a flow rate of 125 cc/min.

When infants in arm A have weaned to the final stage before discontinuation (O2 flow rate <= 125 cc/min, utilized only at night), they will be scheduled for an overnight polysomnography (PSG). These infants will have overnight recording with the Masimo Rad-8 pulse oximeter and serial data recorder on the nights prior to and during the PSG. Final decision regarding safe discontinuation of supplemental O2 therapy will be based on O2 saturation and growth outcomes; infants who do not meet criteria on the first PSG will remain on overnight O2 supplementation and repeat the PSG monthly until they pass.

To determine “Pass” of PSG or to determine ability to wean versus hold on current therapy versus escalate support, strict protocols to analyze O2 saturation status will be followed:

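### In Arm B, recordings around a between-visit step to daytime room air are nocturnal, so they cannot show whether the daytime change was tolerated before the next wean

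*Combined protocol and SAP*

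**What the plan says.** - Section 1 (Abstract): Arm B has the same monthly clinic assessments as Arm A and in addition "will utilize RHO to potentially increase, decrease or maintain oxygen between monthly visits". On stopping oxygen: "To determine discontinuation of oxygen, RHO will be utilized instead of polysomnography".
- Text below Table 1, both arms: once an infant is at 125 cc/min, or was discharged on less, "the next weaning step will be to room air during the day and nocturnal" oxygen only, at 125 cc/min.
- Study Procedures, home recording: the 4-7 day evaluation periods serve to determine "readiness to wean or status post wean, parents will be instructed to use the oximeter continuously during nocturnal sleep periods". The same instruction covers the decision to wean and the check afterwards.
- Table 1, RHO arm (labelled CpOx): oxygen is increased on "INABILITY TO MAINTAIN O2 SAT >93% FOR >95% OF RECORDED TIME". The footnote adds that "CpOx pass and fail will be determined by assessment of recorded oximetry".
- Table 1, standard arm: weaning needs "ABILITY TO MAINTAIN O2 SAT >96% AT WEANED FLOW RATE FOR 20 MINUTES IN CLINIC VISIT CHALLENGE".
- Section 6 (Risks and Discomforts) supports the expectation of less risk in the RHO arm with two reasons: "these infants will continue to have their clinically-indicated, NICU-supplied monitors to ensure safety, and weans will have been made using patient data".

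Two safeguards are written in. Section 4.d keeps monthly oxygen challenges in clinic for all infants until oxygen is discontinued. The clinical home monitor stays in use. The study device only records; it has no saturation alarm and no saturation display.

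**The concern.** The step from 125 cc/min to night-only oxygen changes nothing but the daytime. The instructed recording covers nothing but the night. When Arm B takes this step between visits, the data used to decide it and the data used to check it both describe nights, and by inference from the step definition those nights are on oxygen. The Arm B increase criterion is a share of recorded time, so daytime desaturation cannot trigger it under that instruction.

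Stopping oxygen in Arm B also rests on home recordings, and no section requires a clinic challenge between the daytime step and stopping. An oxygen-dependent preterm infant could therefore be taken off oxygen without having passed any daytime room-air check. For this one step, the patient-data reason in Section 6 does not carry the weight placed on it.

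**Working it through.** The plan gives no figure on this point, so there is none to reproduce. The check sets the rules side by side and then counts dates.

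**1. What each recording can show, for an infant at 125 cc/min**

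| | Day | Night (recorded) |
|---|---|---|
| Before the step | 125 cc/min | 125 cc/min |
| After the step | room air | 125 cc/min |

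The recorded condition is the same before and after. For an infant discharged on less than 125 cc/min, night flow after the step is set at 125 cc/min, so the follow-up night may be on more oxygen than before.

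**2. Who can reach the next decision without a passed room-air challenge**

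- *Above 125 cc/min at the last visit.* The clinic challenge is done at the weaned flow. An infant on 250 cc/min is challenged at 125 cc/min, not in room air.
- *At 125 cc/min at the last visit.* The weaned flow is room air, so a room-air challenge was due. A pass at >96% meets the clinic weaning criterion at that visit. An infant stepped only later will therefore usually not have passed. This is an inference from Table 1.

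**3. Can the next decision come before the next visit?**

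Inputs: data sent every 4-7 days (Section 4f, Arm B only); monthly visits. Assumptions: visits on days 0 and 30, intervals back to back, decisions at the end of an interval.

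*At 125 cc/min at the visit, no turnaround*
- 4-day intervals: steps possible on days 4, 8, 12, 16, 20, 24, 28. The next decision is 4 days later and falls before day 30 for all but day 28: 6 of 7.
- 7-day intervals: days 7, 14, 21, 28. All but day 28: 3 of 4.

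*Above 125 cc/min at the visit, no turnaround.* At least one interval is needed to reach 125 cc/min, so the first date drops out.
- 4-day intervals: days 8 to 28: 5 of 6.
- 7-day intervals: days 14, 21, 28: 2 of 3.

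*Allowing 3 days' turnaround per decision (assumption)*
- At 125 cc/min, 4-day intervals: days 7, 11, 15, 19, 23, 27, next decision 7 days later: 4 of 6.
- At 125 cc/min, 7-day intervals: days 10, 17, 24, next decision 10 days later: 2 of 3.
- From 250 cc/min, three decisions are needed to stop (125 cc/min, daytime room air, off): 3 × (4 + 3) = 21 days, or 3 × (7 + 3) = 30 days. The slower path lands on the visit itself.

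These fractions count calendar dates, not infants.

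**4. Daytime room-air hours without recording**

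Assuming 12 to 16 daytime hours:
- Arm B, step to next decision, turnaround excluded: 12 × 4 = 48 h to 12 × 7 = 84 h, or 16 × 4 = 64 h to 16 × 7 = 112 h.
- Arm A, step at a visit to the next visit: 12 × 30 = 360 h, or 16 × 30 = 480 h.

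Arm A has the longer unrecorded period, but it begins with a passed 20-minute challenge at the new flow. Arm B has no such entry requirement between visits.

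**The case against.** Much can be said for the plan. Night-based weaning is a deliberate choice: Section 3 says the oxygen management protocol rests on nocturnal reference values. Arm B must hold >96% for at least 95% of recorded time to wean, a stricter limit than the >93% PSG pass in Arm A. Neither arm records daytime room air at home. The home monitor stays in place and can alarm, and monthly challenges continue. Adverse-event reporting covers hypoxic events between visits.

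All of this stands, and it limits the point. It does not close the gap. Nocturnal reference values explain the night recordings but supply no daytime data. The monitor's readings feed no weaning criterion, and no section requires their review. Event reporting does not measure saturation.

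Three stronger readings are tempting, and the documents do not support them.

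- *Arm B infants have no daytime room-air data at all.* Those at 125 cc/min at the last visit were due a room-air challenge, and a step taken at a visit is not affected.
- *Arm B is less safe than Arm A.* No daytime desaturation rate is given, and the unrecorded hours above do not point that way.
- *The plan expressly allows stopping one interval after the daytime step.* This is inferred: no minimum time at that stage is stated, and RHO replaces PSG. The text below Table 1 also bases the final decision on saturation and growth. That sentence stands in the Arm A paragraph. If it was meant for Arm B too, waiting for a clinic growth measurement could bring a challenge before stopping, but the plan does not say so.

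Parents are also to be instructed when to record, so training materials might add daytime hours. The protocol's own instruction is nocturnal.

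**Conclusion.** The concern holds in a limited form. For a between-visit step to daytime room air in Arm B, the instructed post-wean recording cannot show whether the change was tolerated, and the written rules do not require a passed daytime room-air check before the next wean, which may be discontinuation.

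The gap is not confined to rare timing. Under the 30-day, no-turnaround assumption, it is open for 5 of 6 or 2 of 3 dates (above 125 cc/min at the visit) and 6 of 7 or 3 of 4 (at 125 cc/min). The number of infants is unknown: at most the Arm B infants who wean, of 98 enrolled per group, and only those stepped between visits.

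The conclusion rests on reading the nocturnal instruction as complete and on the absence of a stated minimum time at the night-only stage. It is worth correcting because it touches a stated safety argument and is cheap to correct. It does not affect the sample size or the definition of any endpoint.

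**What to change.** In Study Procedures and below Table 1, add a rule for Arm B:

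- After a step to daytime room air taken between visits, the next 4-7 day interval also includes a stated minimum of daytime recording in room air on the existing recorder. Eight hours is a natural choice, being the plan's own per-day amount.
- These hours are judged separately from the nights. No further wean is made until saturation is >93% for at least 95% of them. If it is not, the step is reversed.
- The rule is waived if a clinic room-air challenge is passed at or after the step.

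Separate judgement matters. With four nights of 8 hours, 8 daytime hours are 8 / (32 + 8) = 20% of the pooled time. If the nights were entirely above 93%, a quarter of the daytime hours could fail and the pooled share below the limit would be only 0.20 × 25% = 5%, still within the criterion.

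Add a note that the Table 1 limits come from nocturnal reference values, so their daytime use is a working choice. In Section 6, limit the patient-data statement to what the recordings cover.

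The rule protects the next wean; it does not supply daytime data before the step itself. The cost is one added rule, one note and a narrower sentence, some extra recording for families, and possibly slightly longer oxygen duration in Arm B. Between-visit weaning is kept.
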